4. RECRUITMENT AND ENROLLMENT

4.1 Inclusion and Exclusion Criteria: Inclusion criteria for healer clients are 1) 18 year of age or older; 2) able to provide informed consent, 3) not known to be HIV infected; 4) willing to be contacted for monthly follow up for 3 months; and 5) willing to complete an exit survey after 3 months. For the intervention (HIV testing) arm, participants must agree to receive their POC HIV test results. Exclusion criteria include being under the age of 18, incapable of giving informed consent, previously being diagnosed with HIV, being unwilling to receive HIV test results, and

unwilling to participate in the testing intervention. Participating healers are eligible to participate if they meet the UNAIDS definition of traditional healer⁸, and are willing to participate in study procedures. We will select from among healers with patient volume greater than 7 patients per week in order to ensure that participant recruitment progresses in a timely manner for this pilot study.

4.2 Informed Consent: We will obtain written informed consent from both traditional healers (N=20) and their clients (N=500) participating in this study. Participating clients must consent to providing three telephone contact numbers (self, friend, and family member), home address, and permission for the research team access to medical records from the District HIV clinic. In addition, they must consent to a home visit, if they are not reachable for follow up via phone. Healers must consent to keeping a logbook of which patients received HIV testing (intervention arm) or referred to HIV testing (control arm).

4.3 Subject Enrollment: One research assistant will be assigned to each arm of the study and will base themselves at healer practices to consecutively enroll 25 clients from each healer until we reach a sample size of N=500 (four-month enrollment period). The research assistant will assign a unique study ID number to each participant, collect demographic information, and locator information for the participant and two back up contacts. This information will be used for monthly follow-up assessments, and to deliver the exit interview.

4.4 Sample size: N=250 adults will be enrolled in each arm. Community-based HIV-testing in sub-Saharan Africa has excellent uptake (~97%)³⁰; based on these data, we expect 90% uptake of HIV testing in our intervention arm. Assuming HIV prevalence is equivalent to that in our cross-sectional study (9%), we will identify ≥ 20 newly diagnosed HIV-infected patients among our sample of TH clients ($[250 \times .90] \times 0.09 = 20.25$). This aim is exploratory in nature. Sample size will be calculated based on data from an observational census of traditional healers in the study area and will be included in a forthcoming amendment.

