3. STUDY DESIGN

3.1 Design: Previously conducted qualitative work and observational data will inform implementation of a pilot study, offering HIV testing at traditional healer locations in southwestern Uganda. No compensation will be provided for healers in the intervention or control arms of the intervention. We will follow Ugandan National protocols²⁹ to administer voluntary HIV counseling and testing at healer practices in Mbarara District. Clustering for this trial will occur at the level of healer practices. For the intervention arm, we will recruit 250 clients

from ten healer practice locations. For the control arm, we will observe 250 healer clients at ten healer locations undergoing “enhanced standard of care”, where healers will participate in a pre-trial educational session describing community HIV resources available for clients, and how to access them. Enrollment will take place from twenty traditional healer practices, over a period of four months. The follow up period will be three months. Primary outcome for this intervention *will be rates of HIV testing among TH clients (Figure).*

[figure not shown]

Figure. Approach for HIV testing pilot

select half to participate in the intervention arm (N=10); the remaining half will participate in the control arm (N=10). Healers in both study arms will keep a log of participants indicating whether HIV testing was delivered (intervention) or if the participant was referred to HIV testing (control). Many healers have little formal education and describe themselves as “illiterate”; study logbooks will be created accordingly. Research assistants will create stickers with de-identified study identification numbers for each participant. The healer will place the participant ID sticker in the log book (thereby avoiding the need to be able to write numbers); logs will show pictures for receiving point-of-care HIV testing, or not testing (in the intervention arm), or referral to the District HIV clinic for HIV testing, or not referring (for the control group). Healers will circle the corresponding picture for each participant based on the outcome of the session. Research assistants will be on site, or reachable via mobile phone, to answer any questions the healers have about record keeping or study procedures.

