5. STUDY PROCEDURES

5.1 Intervention arm: Healers assigned to the intervention arm (N=10) will attend a half-day training session prior to trial initiation, led by District HIV clinic staff. This training session will demonstrate proper use and disposal of the point-of-care HIV testing kit and provide training regarding patient pre- and post-test counseling. Healers will be instructed to discuss the benefits of linking to HIV care, including importance of initiating treatment for HIV infection, reducing possible transmission to others, and health benefits of starting ART early, as part of post-test counseling. In addition, this training session will discuss resources available at the ISS clinic, including mental health counselors, family and partner support groups, counselors trained to discuss serostatus disclosure strategies, and reproductive health counselors. Supplies for point-of-care HIV testing and biohazard-compliant disposal will be provided to healers at the start of the trial. HIV 1/2 antibody point of care test (Oraquick[©]) will be administered to participants who agree to test. This test is non-invasive, conducted using oral fluids (rather than whole blood), and is FDA-approved for adult use, with results in 20 minutes. Test results are clearly marked with lines, rather than letters or numbers; this test is validated for use by non-medical personnel, with 99.9% specificity and 91.6% sensitivity. Clients with positive tests will be referred to the HIV clinic for Western Blot confirmation, and linkage to care. Following the healer visit, participants will be contacted once per month, for a period of 3 months, to assess for POC test results, and linkage to care for those who test HIV+.

5.2 Control arm: Control arm healers (N=10) will participate in a half-day session prior to trial initiation, led by District HIV clinic staff. This educational session will discuss WHO and Ministry of Health guidelines for HIV testing, who should receive HIV testing and how often, and where to receive it. Participating patients of healers will then receive “enhanced standard of care” as part of the control arm of the trial. Following the visit, study staff will contact the client once per month, for 3 months, to assess for HIV testing since enrollment in the study.

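### Section 4.1 screens intervention clients, but not clearly control clients, on a willingness tied to the primary outcome, so the testing rate and odds ratio can be inflated

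*Combined protocol and SAP*

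**What the plan says.** Section 4.1 lists five client inclusion criteria common to both arms and then adds one for a single arm: "For the intervention (HIV testing) arm, participants must agree to receive their POC HIV test results". The exclusion list contains two further willingness conditions. One, "being unwilling to receive HIV test results", carries no arm label and might cover both arms. The other, "unwilling to participate in the testing intervention", on its wording fits only the arm where testing is offered. No matching condition is written for controls.

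The arm is known when clients are screened. Under section 5.1, "Healers assigned to the intervention arm (N=10) will attend a half-day training session prior to trial initiation", and under section 4.3, "One research assistant will be assigned to each arm of the study". The Summary of Changes of September 2019 alters the healer criteria and the sample size, not the client criteria.

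Other sections expect enrolled intervention clients who do not test. The logbook in section 3.1 has a picture for not testing. In section 5.1 the kit "will be administered to participants who agree to test". Section 4.4 says "we expect 90% uptake of HIV testing in our intervention arm", and the exit survey in section 6.3 covers people who chose not to test. Section 6.2 specifies a multi-level logistic model but names no analysis population. Section 7.5 mentions eligibility checklists, but no tally of approached and refused clients by arm is described.

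**The concern.** A client who will not join a testing intervention, or does not want to hear a result, is plausibly less likely to test over the next three months. Such clients leave the intervention arm at the door, while similar clients can stay in the control arm. Randomisation balances the practices, but the screen acts on clients afterwards, so the arms no longer represent the same population. Under that condition the intervention rate and the odds ratio are too high.

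The screened-out clients have no follow-up, so no model can recover their outcomes, and enrolling more clients under the same criteria would not reduce the bias. Sections 6.1 and 9 make this pilot the basis for a larger cluster-randomised trial, so an inflated effect would carry into its planning.

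A second, smaller matter is the denominator. Section 4.1 appears to keep unwilling clients out, while four other sections expect decliners among those enrolled. A client can agree at entry and decline later, so this is an ambiguity to reconcile, not a strict contradiction.

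**Working it through.** **Inputs from the documents.** Control rate 39%, intervention rate 74%, ICC 0.2, alpha 0.05 and 80% power (Summary of Changes); 10 practices of 25 clients per arm (sections 3.1 and 4.3). A two-sided test is assumed.

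**The plan's own figure.** For 39% against 74%, the two-proportion formula gives 31 per arm. The design effect at 30 per cluster is 1 + 29 × 0.2 = 6.8. Then 31 × 6.8 / 30 = 7.03, rounded up to 8 clusters per arm, or 16 clusters and 480 clients. The stated figure reproduces.

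**Power as planned.** At 25 per cluster the design effect is 1 + 24 × 0.2 = 5.8. SE = √[(0.39 × 0.61 + 0.74 × 0.26) × 5.8 / 250] = 0.0999. The non-centrality is 0.35 / 0.0999 = 3.50, and the non-central t with 18 df gives 91.2% power.

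**Assumptions not in the documents.** Let u be the share of otherwise eligible intervention clients screened out, and v the share of them who would test within three months. The 90% in section 4.4 is uptake among those enrolled, and the 97% there is testing uptake from a cited source, so neither supplies u. I take u = 5%, 10%, 20% and v = 0, 19.5%, 39%; v = 0 gives the largest bias.

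**Bias.** If p is the rate in all otherwise eligible intervention clients, the observed rate is (p − u·v) / (1 − u).

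No true effect (p = 39%), with the two-sided rejection probability in brackets:

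| u | v = 0 | v = 19.5% | v = 39% |
|---|---|---|---|
| 5% | 41.1% (5.4%) | 40.0% (5.1%) | 39.0% (5%) |
| 10% | 43.3% (6.7%) | 41.2% (5.4%) | 39.0% (5%) |
| 20% | 48.8% (14%) | 43.9% (7.2%) | 39.0% (5%) |

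Example: u = 10%, v = 0 gives 0.39 / 0.90 = 0.433, which is 4.3 points too high.

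True rate 74% (odds ratio against 39% = (0.74/0.26) / (0.39/0.61) = 4.45):

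| u | v = 0 | v = 19.5% | v = 39% |
|---|---|---|---|
| 5% | 77.9%, OR 5.5 | 76.9%, OR 5.2 | 75.8%, OR 4.9 |
| 10% | 82.2%, OR 7.2 | 80.1%, OR 6.3 | 77.9%, OR 5.5 |

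Some inflation remains at v = 39%, because those clients still test less often than the 74% average. There is none if screened-out clients would test as often as enrolled ones.

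**Clients lost from view.** Enrolling 250 means approaching 250 / (1 − u) = 263, 278 or 313 otherwise eligible clients, so about 13, 28 or 63 leave one arm with no stated count.

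**Denominator.** Section 4.4's 90% of 250 implies 250 × 0.10 = 25 enrolled intervention clients who do not test. Section 6.2 does not say how they are counted.

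**The case against.** The strongest reply is that the size rests on two invented inputs. On the grid above, with no true effect and u of 5% to 10%, the false-positive probability is at most 6.7%. Only the corner where a fifth are screened out and none would ever test reaches 14%. That is fair: the size is unknown, and the case rests on the one-sided selection itself.

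It can also be said that agreeing to receive a result is not agreeing to test, that decliners are plainly expected, and that the unlabelled exclusion may apply to both arms. All true: the screen does not make the outcome automatic, and on that reading part of it is matched. The exclusion tied to the testing intervention still has no control counterpart.

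Section 4.2 asks clients in both arms for clinic-record access, contact numbers and acceptance of a home visit, so controls are not unfiltered. Because those conditions apply to both arms, they cannot offset one that applies to a single arm.

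Sections 3.1 and 4.4 do point to enrolled clients as the denominator, so that part needs only clarification. A refusal log would allow screened-out clients to be counted as untested in a sensitivity analysis. That bounds the bias but does not remove it, and no such log is described.

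Finally, the odds ratios here are marginal and the rejection probabilities are a cluster-level t approximation, whereas section 6.2 plans a cluster-specific odds ratio. The figures show direction and rough scale; they do not predict the model's output.

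**Conclusion.** The concern holds and should be fixed before enrolment. As written, the plan permits selection after allocation, in one arm, on a trait related to the primary outcome. The direction is upward provided screened-out clients would test less often than enrolled ones.

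At u of 5% to 10%, a true odds ratio of 4.45 would appear as 4.9 to 7.2. With no true effect, the rate would be raised by 0 to 4.3 points, with modest false-positive inflation. These sizes depend on assumed u and v and on the planned ICC of 0.2. The defect in the criteria does not depend on them. The denominator is a secondary point of clarification.

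**What to change.** 1. **Section 4.1:** use the same client criteria in both arms. Delete the intervention-only condition and both unwillingness exclusions. Seek agreement to test and to receive results after enrolment; testing stays voluntary.
2. **Section 6.2:** state that all enrolled clients are analysed by allocated practice, and that those who decline count as not tested unless they test elsewhere within three months. Align sections 3.1, 4.4, 5.1 and 6.3 with this.
3. **Screening log:** record approached, eligible, refused and enrolled clients by arm, and report refusals by arm. The checklist in section 7.5 can carry this.
4. **Consent:** the wording need not be identical if identical wording would prompt control clients to test.
5. **If a willingness condition is kept:** ask it in the same way in both arms before the client learns the arm. The result then applies to willing clients only, and the question may itself prompt controls to test.

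**Cost.** An amendment to sections 4.1 and 6.2, a simple log, and a less favourable intervention rate. If 74% already describes all clients, there is no power cost. If it describes willing clients only, the all-client rate is 0.74 × (1 − u) + u·v, and power falls from 91.2%:

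| u | v = 0 | v = 19.5% | v = 39% |
|---|---|---|---|
| 5% | 83% | 85% | 88% |
| 10% | 71% | 78% | 83% |

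Power reaches 80% at an all-client rate of 69.3%, which corresponds to u of about 6.4%, 8.6% or 13.4% for the three values of v. The sponsor should say which population the 74% describes and restate the power if the target rate changes.

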Loss of confidentiality will also be minimized through de-identification of study data. Only the participant's study ID number will appear in the paper or computer-generated files. The key to participants' code number will be encrypted in a computer file, which will be kept in locked offices at MUST. Only [name] (PI), [name], and the research assistants will be able to unencrypt these computer files. In addition, all study staff will be asked to sign a confidentiality pledge. In signing this pledge, the researcher agrees not to divulge the identity of any study participant outside of the study team, nor discuss the particularities of any participant's story with anyone outside the study team.

Study participants may feel reticent to share information about sexual orientation, and this may be a limitation of our study approach. However, the vast majority of HIV transmission in sub-Saharan Africa occurs through heterosexual intercourse³¹, and therefore we do not anticipate that unwillingness to disclose homosexual orientation will negatively impact our data collection or results. Participants will be reminded during questionnaire administration that answers regarding sexual orientation will be kept between study participant and research team, and that numerous mechanisms are being undertaken to safeguard their identity, including de-identification of study data.

For potential participants for the testing intervention arm who presents with sexual partners, we will carry out private, individual recruitment and consent, and request if we could include the partner in the HIV testing process. If permission is granted by the participant, then we will 1)

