Changes to the inclusion criteria for traditional healers were submitted as follows:

We predetermined an 8-kilometer one-way travel distance to the ISS HIV clinic as the geographic boundary within which to include traditional healers as recruitment locations for this trial. This distance was established as a walking distance to one or more HIV testing resource are centralized. Twenty-five traditional healers were identified within this area. Traditional healers will be considered eligible for participation as cluster sites if they are 1) were aged 18 years or older; 2) have a practice located within eight kilometers of the ISS clinic; 3) were identified in the 2018 population-level census of traditional healers in Mbarara District; and 4) delivered care to at least 7 patients per week. The final criterion excludes healers with average patient volumes in the lowest quartile in order to ensure that participant recruitment progresses in a timely manner for this pilot study.

Changes to the sample size were submitted as follows:

We assumed a baseline testing rate of 39% among our population based on Ministry of Health population-level data⁸. We predicted that the HIV testing rate would increase by 35% to 74% in the intervention arm. Using intracluster correlation coefficient estimate = 0.2, we calculated that we would need to include a minimum of 16 clusters total, with an average of 30 participants recruited per cluster (total sample size of 480 participants), to detect this difference, with 80% power and alpha = 0.05. We plan to recruit 20 healers as clusters in our study to maximize analytical power. Target enrollment number for clients will be 250 per study arm, divided equally among cluster sites in each study arm.

Secondary outcome of “variables that predict HIV testing” was also removed

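### Arms are known before clients are enrolled, and nothing in 4.1 or 4.3 prevents or measures the entry of people who attend an intervention practice because HIV testing is offered there

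*Combined protocol and SAP*

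**What the plan says.** **Allocation comes first and is open.** Sections 5.1 and 5.2 have healers in each arm attend their own arm's session before the trial begins. For the intervention arm, "Supplies for point-of-care HIV testing and biohazard-compliant disposal will be provided to healers at the start of the trial". Section 4.3 gives each arm its own research assistant. Section 7.2 contains the phrase "For potential participants for the testing intervention arm who presents with sexual partners", so the arm is known when a person is approached for consent.

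**Clients come second.** The research assistants "base themselves at healer practices to consecutively enroll 25 clients from each healer until we reach a sample size of N=500". Section 3.1 adds: "Enrollment will take place from twenty traditional healer practices, over a period of four months".

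**Entry rules.** Section 4.1 begins "Inclusion criteria for healer clients are 1) 18 year of age or older; 2) able to provide informed consent". It continues with no known HIV infection, willingness to be followed monthly for three months, and willingness to complete an exit survey. The term healer client is not defined, and no criterion concerns why the person came. The enrolment data listed in 4.3 are demographic and locator information.

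**Outcome and analysis.** The primary outcome is the rate of HIV testing among healer clients at three months. Section 6.2 compares arms by a two-level logistic model, with clients nested within healers.

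**The concern.** In a cluster-randomised trial that recruits individuals after the clusters are allocated, the arm can affect who arrives. Here a client's arm follows entirely from the healer visited. Someone who learns that a practice offers on-site testing, and goes there for it, meets every criterion in 4.1 and counts as a tested healer client. Control practices have no on-site test to attract such a person. Consecutive enrolment limits picking by the research assistant but does not stop self-referral.

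The primary comparison would then mix two things: a change in testing among people who use healers anyway, and a change in who attends. The random effect for healer does not separate them. Adjustment for demographics would not do so either unless the reason for the visit is known. This matters because section 6.1 presents the results as the basis for a larger trial.

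**Working it through.** **Inputs**

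- Control rate, from the Summary of Changes to Protocol: "We assumed a baseline testing rate of 39% among our population based on Ministry of Health population-level data".
- Design intervention rate, same place: "We predicted that the HIV testing rate would increase by 35% to 74% in the intervention arm".
- Uptake, from section 4.4: "we expect 90% uptake of HIV testing in our intervention arm".
- From the Summary of Changes: ICC 0.2, 30 per cluster, 80% power, alpha 0.05 (two-sided assumed here). The planned trial has 20 healers and 250 clients per arm, so 25 per healer.
- Share s of intervention enrolees who came for the test: not in the documents. Assumed 10, 20 and 30%, all of them tested.

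**Step 1. The plan's own figure.** With a mean rate of 0.565, the number per arm before clustering is [1.96·√(2·0.565·0.435) + 0.842·√(0.39·0.61 + 0.74·0.26)]² / 0.35² = (1.374 + 0.552)² / 0.1225 = 30.3, rounded up to 31. The design effect is 1 + 29·0.2 = 6.8. Then 31·6.8 = 210.8, and 210.8/30 = 7.03, so 8 clusters per arm: 16 clusters and 480 clients. This matches the plan. With 10 healers of 25 per arm, power is about 92%.

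**Step 2. The bias.** Observed intervention rate = s + (1 − s)p, where p is the rate among ordinary clients. The excess over p is s(1 − p).

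| p among ordinary clients | s = 10% | s = 20% | s = 30% |
|---|---|---|---|
| 90% (section 4.4) | 91.0% (+1.0) | 92.0% (+2.0) | 93.0% (+3.0) |
| 74% (design) | 76.6% (+2.6) | 79.2% (+5.2) | 81.8% (+7.8) |
| 39% (no effect) | 45.1% (+6.1) | 51.2% (+12.2) | 57.3% (+18.3) |

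**Step 3. The odds-ratio scale.** Section 6.2 reports an odds ratio. Crude odds ratios against 39%, taken directly from these proportions, move as follows for s = 10, 20 and 30%:

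- p = 90%: from 14.08 to 15.81, 17.99 and 20.78.
- p = 74%: from 4.45 to 5.12, 5.96 and 7.03.
- p = 39%: from 1.00 to 1.28, 1.64 and 2.10.

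The model's within-healer odds ratio will differ somewhat from these.

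**Step 4. Scale.** To produce the whole 35-point difference with no real effect, s would have to be 0.35/0.61 = 57%. In a cluster of 25, three test-seekers are 3/25 = 12%.

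**The case against.** The strongest reply is that the mechanism is only a possibility.

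- No passage says that testing at healers is advertised or that anyone will come for it. Nor is the test at the practice stated to be free; that is inferred from study-provided supplies.
- Section 7.2 describes no-cost testing at the local HIV clinic, and the Summary of Changes places participating healers within 8 km of the ISS HIV clinic.
- Trial entry is a burdensome way to obtain a test: several telephone contacts, a home address, access to clinic records and consent to a home visit (4.2).
- The four months cover all twenty sites. At 7 patients a week, a practice could fill in 25/7 = 3.6 weeks if nearly all agree, leaving little time for word to spread.
- Section 4.1 requires intervention clients to accept their results and excludes those unwilling to take part in testing. That pushes p up and so shrinks s(1 − p).
- Attracting new testers may be seen as part of the programme's benefit.

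Most of this stands as a limit on size. A reader might infer a serious false-positive risk from the 39% row: by a normal approximation with design effect 5.8, the chance of a significant result favouring the intervention is about 8, 20 and 40% at s = 10, 20 and 30%, against 2.5% nominal. Those figures need both an assumed s and no effect at all on clients already screened for willingness. The documents support neither.

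The reply does not remove the gap. The label healer client suggests ordinary attenders but does not define them. Section 1 argues that healers are more accessible than biomedical providers, so nearby clinic testing does not rule out self-referral. The Summary of Changes identifies only 25 healers in the area, of whom 20 are to take part, so residents may be able to choose between practices. Attracting new testers may be a real benefit, but the planned comparison cannot tell it from changed behaviour among existing clients.

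**Conclusion.** The point holds as a risk of recruitment bias that the plan neither prevents nor is stated to measure. Its direction is toward the intervention. Its size cannot be derived from the documents: for an assumed s of 10 to 30%, with all test-seekers tested, it is 1 to 3 points at 90% uptake, 2.6 to 7.8 at 74%, and 6.1 to 18.3 with no effect. At the plan's own rates it is modest beside a 35-point target.

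Two stronger readings are not supported. One is that test-seekers will enter and inflate the rate; the documents show only that they could. The other is that the reason for the visit is not recorded; 4.3 does not list it, but the enrolment questionnaire is not among the documents. The point warrants a cheap addition before enrolment, because the reason for attending cannot be reliably recovered afterwards.

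**What to change.** - **4.1:** define a healer client, identically in both arms, as someone attending for the healer's own services.
- **4.3:** have the research assistant ask every consecutive attender in both arms, before the study or HIV testing is mentioned, one neutral open question: the main reason for today's visit, and whether the person has attended this healer before. Log the answers by healer. Do not ask control attenders whether they have heard that testing is offered there, since that could itself prompt testing. Do not leave exclusion to the judgement of an unblinded, arm-specific research assistant; apply the definition to the logged answer by a rule written in advance.
- **6.2:** pre-specify an analysis of the primary outcome restricted to clients whose recorded reason was healer care. Report it beside the analysis of all enrolees, with the number of test-seekers by arm.

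**Cost:** one or two extra enrolment questions and a few sentences of text. Stated reasons are self-reported and may be mixed or imprecise, so the restricted analysis reduces the bias rather than guaranteeing its removal. The loss of precision is small. At s = 30%, 175 of 250 intervention clients remain, 17.5 per healer, with design effect 1 + 16.5·0.2 = 4.3. The effective number is 175/4.3 = 40.7, against 250/5.8 = 43.1 for the full arm.
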